7.4.2. Discussion of Study Population

The study eligibility criteria are in alignment with the prescribing information in the FDA approved labels for both ABL and TPTD and include women with postmenopausal osteoporosis. Patients with secondary osteoporosis, Paget's disease, as well as those who would not be candidates for the anabolic drug due to high morbidity burden or high risk of mortality (ie, malignancies), are excluded. Patients with prior alendronate therapy will be included because almost half of the population of patients new to anabolic therapies have previously used bisphosphonates. Although the treatment guidelines suggest initiation of therapy with bone building agents followed by antiresorptive agents to maintain bone, market access criteria requiring step therapy and prior authorization for anabolic agents result in the use of anabolic agents later in the course of disease progression and severity ([McClung et al, 2017](#); [Tsourdi et al, 2017](#); [Zanchetta et al, 2018](#)). Limiting the study population to those without any prior therapy would significantly reduce the size of the study population. Therefore, subgroup analyses will be performed based on prior use of osteoporosis treatment. Furthermore, there is no evidence indicating diminished treatment response to anabolic therapy following alendronate use ([Cosman et al, 2017](#); [Langdahl et al, 2018](#)). As such the study criteria provide a suitable population for evaluation of the effectiveness and cardiovascular safety of ABL without compromising sample size yet minimizing potential selection biases.

7.5. Data Sources

This study will use anonymized patient level data from PRA's Symphony Health IDV database, including the enhanced hospital data. PRA's IDV database is a large nationally representative claims-based database. The database cross-sectionally covers over 80% of the population in the USA (approximately 300 million lives) annually. It includes claims submitted to all payer types, including commercial plans, Medicare, and Medicaid. In terms of the pharmacy claims, it captures approximately 92% of the retail and 65% specialty pharmacy claims, and approximately 68% of mail order claims. For medical claims, it covers approximately 60% of professional claims in an outpatient setting. Medical claims are open unadjudicated claims. Mortality data recorded on the hospital (medical facility) discharge status covers about 1/3 of the total death records. According to National Center for Health Statistics data published on CDC wonder (CDC, 2021), 35% total deaths in 2019 happened at medical facility which includes hospital inpatient, outpatient or emergency room, death on arrival or unknown status. This number is slightly high (37%) for cardiovascular death (cause of death is I00 to I99 in ICD-10). For women at age 50, 54% percentage of cardiovascular death occurred in medical facilities. The data are de-identified, in compliance with Health Insurance Portability and Accountability Act (HIPAA) guidelines, with stable unique identifiers to allow for longitudinal tracking over time. The terms of the Research Exception provisions of the Privacy Rule, 45 Code of Federal Regulations (CFR) Part 164.514(e) exempts Institutional Review Board (IRB) approval for this nonexperimental study, which is fully HIPAA compliant.

Table 3 summarizes the calendar time range used to ascertain cohort entry (index date), as well as the calendar time range of data available for pre-index- assessment windows and post-index follow up (study period). The data source name and version are identified, as well as any sampling criteria applied (for example, the data cut only includes patients with a diagnosis of diabetes). If data linkage is involved, provide a citation or an appendix with description of the linkage (how, performance characteristics).

All individual data will be de-identified and signed data license agreements will be in place for all data sources.

Table 3 Metadata About Data Source and Software

Data Sources:	PRA (Symphony Health's) Integrated Dataverse (IDV) database.
Study Period:	May 1, 2012 to January 31, 2021
Eligible Cohort Entry Period:	May 1, 2017 to June 30, 2019
Data Extraction Date/Version:	June – 2021 via a single data pull
Data Sampling/ Extraction Criteria:	Refer to Section 7: Research Methods for study design, treatment cohorts, evaluation periods, and subject selection criteria.
Types of Data:	Medical, hospital and prescription claims data.
Data Linkage:	No data linkage will be required.
Data Conversion:	No data conversion will be required.
Software to Create Study Population:	[REDACTED] software used to connect to the Cloudera Hadoop CDH 7.1.4-1 database for data extraction. R software might be used for propensity score matching.

7.6. Variables for Data Extraction

The endpoints to be assessed in this study are provided in [Section 5.2](#).

7.6.1. Demographics and Baseline Variables

Potential confounding variables include the following:

- Demographic variables (age, race/ethnicity if available)
- Insurance information (commercial, Medicare, Other)
- Patient geographic region (majority coverage includes West, South, Northeast, and Midwest)
- ABL and TPTD prescriber physician's specialty (endocrinology, rheumatology, surgery, family medicine, internal medicine, nursing related, obstetric
- Index date year quarter

7.6.2. Risk Factors

Conditions associated with increased risk of fractures or falls ([Camacho et al, 2020](#)), including pre-index fracture history, for which data are available in administrative claims, will be assessed by the presence of ICD codes in the claims database. History of co-morbidities associated with an increased risk of falls and/or fractures, as well as those conditions associated with poor bone health, will be assessed (see [Section 7.6.3](#) for the list of co-morbidities).

Data for medical history associated with a high risk of cardiovascular events will also be extracted: MI, stroke, and heart failure.

7.6.3. Co-morbidities

Known co-morbidities identified in the target patient population that will be included in this retrospective cohort study are:

- **Comorbidities that increase the risk of fall:** prior history of any stroke, mobility impairments, vision impairments, hearing impairments, Parkinson's disease, muscle atrophy, muscle weakness, or sarcopenia.
- **Comorbidities that lengthen healing time:** diabetes, liver disease, or renal disease.
- **Other comorbidities associated with an increased risk of fractures or requiring treatment associated with an increased fracture risk:** hypertension, dyslipidemia, arthritis, respiratory diseases including asthma and chronic obstructive pulmonary disease, depression, anxiety, sleep disorders, cardiovascular disease, hypothyroidism, obesity, or gastrointestinal disorders.

7.6.4. Osteoporosis Treatment History

Pharmacy claim for previous use of any of the following medications:

- Bisphosphonates (ie, alendronate, ibandronate, risedronate, or zoledronate)
- Denosumab
- Oral glucocorticoids
- Hormone replacement therapy

7.6.5. Concomitant Medications

Concomitant osteoporosis medications expected to be used in the target patient population include the following:

- Bisphosphonates (ie, alendronate, ibandronate, risedronate, zoledronate)
- Denosumab
- Hormone replacement therapy

7.6.6. Anabolic Drug Exposure

Cohort anabolic drug exposure is defined as a prescription filled for either abaloparatide (ABL cohort) or teriparatide (TPTD cohort). Exposure will be determined using pharmacy claims data in the NDC Codes and HCPCS Codes for Medications. For a list of codes please see Appendix 5.

7.6.7. Outcomes

Both effectiveness and cardiovascular safety outcomes will be assessed for patients with 18 months of follow-up data after their index date. Cardiovascular safety outcomes will be evaluated during the treatment period which is from index date to the last prescription anabolic drug possessed within the 18 months after the index date, regardless of the anabolic drug possession gap between any 2 prescription fills.

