5.2. Objectives and Endpoints

Objectives	Endpoints

Primary Objective:
 
 • To evaluate the effectiveness of ABL for the treatment of osteoporosis in postmenopausal women in the real-world healthcare setting in the United States of America (USA) compared with TPTD using the same cohort of propensity score (PS)-matched patients. 	
Primary Endpoint:
 
 • Time to the first incidence of nonvertebral fracture (hip, pelvis, shoulder, radius or ulna, wrist, femur, tibia or fibula, ankle) within the 18 months after treatment initiation.

Secondary Objective:
 
 • To evaluate the cardiovascular safety of ABL for the treatment of osteoporosis in postmenopausal women in the real-world healthcare setting in the USA compared with TPTD using the same cohort of PS-matched patients. 	
Secondary Endpoints:
 
 • Time to the first incidence of the composite endpoint of nonfatal MI, nonfatal stroke, or in-hospital cardiovascular death within the 18 months after treatment initiation and while still on therapy. • Time to the first incidence of the composite endpoint of nonfatal MI, nonfatal stroke, heart failure or in-hospital cardiovascular death within the 18 months after treatment initiation and while still on therapy.

Exploratory Objective:
 
 • To further evaluate the effectiveness and cardiovascular safety of ABL for the treatment of osteoporosis in postmenopausal women in the real-world healthcare setting in the USA compared with TPTD using the same cohort of PS-matched patients. 	
Exploratory Endpoints:
 
Efficacy
 
 • Time to the first incidence of hip fracture within the 18 months after treatment initiation. 
Safety
 
 • Time to the first incidence of MI • Time to the first incidence of stroke • Time to the first incidence of in-hospital cardiovascular death • Time to the first incidence of heart failure

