7. RESEARCH METHODS

7.1. Study Design

This will be a retrospective observational study using administrative data for the period from May 2012 to January 2021. The most recently available data at the time of data extraction will be used. This study will use anonymized patient claims data from PRA's Symphony Health Patient Source Integrated Dataverse (IDV) database with the inclusion of enhanced hospital data, which are claims and remittance from the inpatient hospital setting and proprietary Patient Transactional Dataset (PTD) claims and prescription data, to apply the inclusion/exclusion criteria for patient selection (see [Section 7.4.1](#)) to form the data set.

Figure 1 Study Design Schematic

ABL= abaloparatide; TPTD = teriparatide.

The **Identification Period** is the period of time during which subjects will be identified based on their index date (01 May 2017 to 30 June 2019).

The **Index Date** is the date on which the subject filed their first claim for a prescription for either ABL or TPTD during the identification period.

The **Pre-index Period** consists of the 5 years before the Index Date during which medical history was available for the subject.

The **Post-index Treatment Period** consists of the 18 months plus 30 days follow-up after the initiation of treatment with anabolic drug (ABL or TPTD) on the index date and continuing for the duration of treatment.

Treatment Cohorts

This is a real-world observational study. Treatments will not be assigned. Instead, cohorts are defined as follows:

- **Abaloparatide Cohort:** Patients who filled ≥ 1 prescription for ABL (TYMLOS) as their index medication during the identification period.

- **Teriparatide Cohort:** Patients who filled ≥ 1 prescription for TPTD (Forteo) as their index medication during the identification period.

Evaluation Period

The date of the first claim for either ABL or TPTD during the identification period (between May 1, 2017 and June 30, 2019) will be considered the index date.

- The medication received on the index date will be considered the index medication.
- Treatment duration may continue for up to 18 months (540 days) after the index date.
- The evaluation of outcomes will start immediately after treatment initiation and will continue for 18 months after the index date for both effectiveness and cardiovascular safety evaluation regardless of the drug possession gap between any 2 prescription fills.

Primary Analyses

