7.6.7.2. Evaluation of Cardiovascular Safety

Evaluation of cardiovascular safety outcomes will be carried out for patients who have 18 months of follow-up data from their index date while on treatment with ABL or TPTD. The following data variables will be extracted:

- End of treatment date which is the last prescription date + supply day
- Date of the first incidence of MI
- Date of the first incidence of stroke
- Date of the first incidence of heart failure
- Date of in-hospital cardiovascular death
- Date of all-cause in-hospital death

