7.8.3. Analysis Populations

Analysis population are all patients meeting the study inclusion/exclusion criteria and selected after propensity matching. The same matched population will used for both effectiveness and safety analysis.

The effectiveness evaluation will be conducted using an ITT analysis, meaning that the first fracture event during the 18 months (+ 30 days follow-up) after the index date will be summarized regardless of when treatment ended. Cardiovascular safety outcomes will be evaluated using an As-Treated (AT) analysis based on only events occurring during the treatment period which is from the index date to the last prescription anabolic drug obtained within the 18 months after the index date, regardless of the anabolic drug possession gap between any 2 prescription fills.

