7.8.7. Safety Analyses

A Cox proportional hazards model will be used for the time to first cardiovascular event. HR and 95% CIs will be presented.

The ICD-10 diagnosis from the hospital claim and physician claim will be used to derive post-index myocardial infarction (MI) (I21.x, I22.x), stroke (I61.x – I63.x), or heart failure (I50.x, excluding I50.x2, I50.8x). Hospital discharge status code (20 to 29 or 40 to 42) will be derived for in-hospital death. A detailed code list is provided in [Appendix 3](#). Subjects with in-hospital cardiovascular death derived from indirect approach 2 ([Xie et al, 2018](#)) will be included in the analyses. 2018 ICD-10 CM and General Equivalence Mappings (GEMS) from the Centers for Medicare & Medicaid (CMS) ([will be used to translating ICD-9 CM to ICD-10 CM \(CMS, 2018\)](#)).

The As-Treated (AT) analysis will be conducted for the safety evaluation. The first incidence of a cardiovascular event after the index date and before the 30 days after the end of treatment will be analyzed.

A cardiovascular event is the first incidence of the composite endpoint of nonfatal MI, nonfatal stroke, or in-hospital cardiovascular death; the first incidence of the composite incidence of nonfatal MI, nonfatal stroke, heart failure or in-hospital cardiovascular death; or the first incidence of MI, stroke, heart failure, or in-hospital cardiovascular death separately.

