7.8.8. Anabolic Drug Exposure

The overall duration of cohort anabolic drug exposure will be summarized for PS-matched patients.

Overall Duration of Anabolic Drug Exposure (day) = Date of last anabolic drug prescription fill + Supply days – index date + 1

Consecutive treatment duration is determined from the index date to the last drug supply date without any gap exceeding 60 days.

Because the efficacy and safety evaluations are limited to an 18-month period, the overall duration of the anabolic drug exposure will be cut off at 540 days, even if the patient used the anabolic drug (ABL or TPTD) for > 18 months.

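### The as-treated cardiovascular window bridges drug gaps by looking ahead to a later fill, so part of the counted time is immortal for CV death

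*Combined protocol and SAP*

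**What the plan says.** Both secondary endpoints are on-therapy composites. Section 5.2 defines the first as the "composite endpoint of nonfatal MI, nonfatal stroke, or in-hospital cardiovascular death within the 18 months after treatment initiation and while still on therapy"; the second adds heart failure. Four places then fix the as-treated window.

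- Section 7.6.7 runs it "from index date to the last prescription anabolic drug possessed within the 18 months after the index date, regardless of the anabolic drug possession gap".
- Section 7.8.3 repeats the rule with a different verb: "the last prescription anabolic drug obtained within the 18 months after the index date, regardless of the anabolic drug possession gap between any 2 prescription".
- Section 7.6.7.2 defines the "End of treatment date which is the last prescription date + supply day".
- Section 7.8.7 adds the tail: "The first incidence of a cardiovascular event after the index date and before the 30 days after the end of treatment will be analyzed".

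Read together, the window closes at last fill + supply days + 30 days, and every gap before the last fill is bridged, however long.

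Two other statements bear on this. Section 7.8.8 has a gap rule ("Consecutive treatment duration is determined from the index date to the last drug supply date without any gap exceeding 60 days"), but it defines consecutive exposure and does not end cardiovascular follow-up. Section 7.1 says that outcome evaluation "will continue for 18 months after the index date for both effectiveness and cardiovascular safety evaluation regardless of the drug possession gap", which is a different window. Section 7.1 also names as-treated as the primary safety analysis.

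**The concern.** Whether a woman is at risk on a given day should be decidable from what has happened up to that day. Under this rule a gap day counts as treated only if a fill occurs later, and refilling requires that she be alive. Time beyond supply + 30 days thus enters the denominator only for women who survived it, which is immortal time in the usual sense.

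Both secondary composites and the four exploratory cardiovascular endpoints use this window in the as-treated analysis, and cardiovascular safety is the study's only secondary objective. The component hit without condition is in-hospital CV death. If lapse-and-return patterns differ between ABL and TPTD, the arm with more bridged time would look safer than it is.

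No planned analysis removes the problem. The exposure-duration analyses in Section 7.8.10.1 themselves select on future fills. Those in Section 7.8.10.2 change the event definition, not the window. Propensity matching (Section 7.8.5) uses pre-index variables, so it does not guarantee equal refill behaviour afterwards.

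**Working it through.** **No plan figure to reproduce.** The documents state no cardiovascular rate, gap distribution or power for this analysis. The only power figure (Section 7.8.1.2) is for fracture. On the absolute-difference scale it reproduces: 2 × 0.035 × 0.965 × (1.960 + 1.645)² / 0.0105² = about 7,962 per arm, against 8,000. It does not bear on this point.

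**Applying the rule.** Four women each fill 30 days of drug on day 0 and then lapse.

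- Dies of a CV cause in hospital on day 150. Treatment ended on day 30, the window closed on day 60, and the death is not counted.
- No event, refills on day 300. Days 60 to 300, 240 days, enter the denominator.
- MI on day 150, refills on day 300. The MI counts.
- MI on day 150, never refills. The window closed on day 60 and the MI does not count.

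**Formula.** Let b be the share of counted person-time lying in bridged gaps beyond supply + 30 days. Outside that time, risk status depends only on past fills, so the rate there is the true rate. Inside it, the counted death rate is zero. Hence, with constant hazards:

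- observed / true CV death rate = 1 − b;
- composite, if nonfatal events do not affect refilling: about 1 − f·b, where f is the fatal fraction of events;
- composite, if every nonfatal event stops refilling: about 1 − b.

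**Simulation.** All of these inputs are assumptions: 30-day fills, exposure cut at 540 days plus the 30-day tail, 5% discontinuation per fill, CV death 0.5% per year, nonfatal MI or stroke 1.5% per year (f = 0.5/2.0 = 0.25), and exponential gap lengths. The table gives observed / true rate under the planned window. The last three columns show how often a nonfatal event stops refilling.

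| Refills with a gap, mean gap | CV death | Composite: never | Composite: half | Composite: always |
|---|---|---|---|---|
| 5%, 90 days | 0.93 | 0.99 | 0.96 | 0.93 |
| 10%, 90 days | 0.89 | 0.98 | 0.94 | 0.89 |
| 10%, 150 days | 0.85 | 0.96 | 0.91 | 0.86 |
| 20%, 150 days | 0.77 | 0.94 | 0.86 | 0.76 |

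For nonfatal events alone the ratios are 0.99-1.01 (never), 0.97-0.88 (half) and 0.94-0.76 (always). With no gaps the planned window gives 0.99-1.03, so differences of 1-3% are within simulation noise. The formula agrees: b = 0.23 gives 0.77 for death and 1 − 0.25 × 0.23 = 0.94 for the composite when refilling is unaffected.

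**Window without look-ahead.** Ending follow-up 30 days after supply runs out, at the first gap over 30 days, brings every ratio to 0.98-1.02.

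**Hazard ratio.** Equal factors in the two arms cancel. If one arm had the mildest death-rate factor and the other the heaviest, a true HR of 1 would read 0.77/0.93 = 0.83 or 0.93/0.77 = 1.21, depending on which arm has more gaps.

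**The case against.** Four points on the other side have force.

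- A reader might infer that the window stops at the last fill, or that bridged gaps are event-free for every endpoint. Neither is so. Supply days and 30 days are added, and a nonfatal event in a gap counts once the woman refills. If events do not alter refilling, nonfatal rates are essentially unbiased and the composite loses only about 1-6%.
- A reader might infer that the HR is biased, or biased in favour of ABL. The documents do not support this. Section 6.3 reports similar disease characteristics and comparable market access for the two drugs, and gives no reason to expect different gap patterns. It does not exclude them either, and the plan does not compare gaps by arm.
- Precision is limited. Assuming the 0.6% MACE proportion quoted for TPTD in ACTIVE (Section 6.2.3), 16,000 women give at most 96 events. The SE of the log HR is then about 2/√96 = 0.20, and the confidence interval spans a factor of about exp(1.96 × 0.204) = 1.5 each way. This limits the practical weight of a modest bias but does not excuse a systematic one. No cardiovascular margin or decision rule is set.
- A reader might infer that the defect arises whichever end date is used. It does not. The 18-month window in Section 7.1 has no look-ahead. That reading, however, contradicts the on-therapy endpoints (Section 5.2) and the as-treated analysis (Sections 7.1, 7.6.7, 7.8.3 and 7.8.7), which have the weight of the text.

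What remains is the zero counted death rate in bridged time, which follows from the definition and needs no assumption about behaviour.

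**Conclusion.** The concern holds for CV death without condition and for the composites through it. For nonfatal MI, stroke and heart failure it holds only to the extent that an event stops refilling. The direction for death is certain whenever bridged time exists. The size is unknown because the documents contain no gap data. Under the assumed patterns the CV death rate is understated by about 7-23% and the composite by about 1-24%, the lowest values being within simulation noise. An HR effect requires gap patterns that differ by arm and should be stated as a possibility, not a finding. The plan should be changed because the defect affects the secondary endpoints, no planned analysis corrects it, and the repair is inexpensive.

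**What to change.** In Sections 7.6.7, 7.6.7.2, 7.8.3 and 7.8.7, define as-treated follow-up without reference to later fills. Censor each woman at the first date on which 30 days have passed since supply ran out with no new fill, without re-entry. For the cardiovascular analyses, delete the clause that disregards gaps between fills.

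The tolerated gap and the post-supply tail must have the same length. The 60-day rule of Section 7.8.8 combined with a 30-day tail would still make days 31-60 of a gap conditional on refilling.

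If start-stop intervals with re-entry are preferred, state that a woman whose first event falls in an off-drug gap does not re-enter for that endpoint. Otherwise a later claim carrying the same code could be taken as her first event.

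Reconcile the 18-month statement in Section 7.1 with the as-treated definition there and in the sections above. Add an 18-month ITT cardiovascular analysis as a sensitivity analysis.

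The cost is wording plus programming on fill dates and supply days that the plan already uses. Event counts fall slightly and person-time is reduced, because events and time in bridged gaps, and on treatment after a gap, no longer count.
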